#### Summary of changes in Version 2:

- 1. Page 14 table 1 Sedation scores and follow-up on POD3 were removed from table 1 (to conform to the protocol text). Evening bladder scan timing description changed, since the is no evening drug administration
- 2. Page 15 inclusion criteria added revision arthroplasties and general anesthesia
- 3. Page 15-Removed the requirement for PCA, added a general requirement for post-op opioids
- 4. Page 17-The need for straight catheterization in PACU and/or on the floor when it is medically indicated (volumes exceeding 400 ml) will be recorded by the study team and subsequent bladder scan will therefore not be done. Postoperatively, all patients will be given intravenous or oral opioids for pain control. Clinicians will adjust analgesic management as necessary in an effort to adjust verbal response pain scores to less than 4.
- 5. Bladder scan to be done on the evening of surgery.
- Patient clinically does not have ileus if he is passing gas (no need to record /look for bowel sounds)
  Summary of changes in Version 3:
- 1. Page 16 Exclusion criteria- removed antihistamines, phenothiazines, antidepressants and antipsychotics Summary of changes in Version 4:
- 1. Page 14 Secondary Aim Hypothesis changed ORSDS questionnaire from being asked on first, second, and third post-operative days to just the first two post-operative days.
- Page 15 Study Overview wording added to maintain consistency with previous revisions for including knee surgery cases
- 3. Page 15 Table bladder scanning during PACU stay omitted. Far right column in version 3 that represented nothing was removed for clarification.
- Page 22 Secondary and exploratory analysis ORSDS was changed to only being asked on post-operative days 1 and 2. Myles Quality of Recovery scale was changed to only be asked on either post-operative day 2 or the day of discharge.
- 5. Removal of requirement for bladder scanning to be done on the evening of surgery

#### Summary of changes in Version 5:

- 1. Page 21 "POD 1 to 3" changed to "POD 1 and 2" regarding ORSDS follow up
- 2. Page 21 "POD 1 and 3" changed to "POD 2" regarding Quality of Recovery follow up
- 3. Page 21 Added clause regarding loss of follow up rate and the need for extra patients to reach planned power to 136 patients with 2 pilots

Appendix

#### INTRODUCTION

Pain is a psychological sensory experience, which is caused by various factors. Surgery results in tissue damage which leads to postoperative pain. Studies in recently developed animal models of postoperative pain have advanced our knowledge of the mechanisms of pain resulting from surgical incision and associated tissue injury. Postoperative pain results from combination of nociceptive and inflammatory components[1]. The nociceptive component results from activation of peripheral sensory neurons damaged by surgical incision, and fades gradually as tissues heal. The inflammatory component enhances pain sensitivity via release of mediators from the surgically injured tissue. Central neuronal sensitization also seems to contribute to postoperative pain and hyperalgesia. [1, 2] Due to aforementioned mechanisms, pain is present in spontaneous resting at the site of surgery plus surrounding tissues. Movement or touching of the wound site, breathing, coughing, and gastrointestinal motility can all evoke pain. Unrelieved postoperative pain leads to multiple physiological and psychological consequences, which worsen outcomes. For example, inadequate perioperative analgesia is associated with myocardial ischemia, impaired wound healing, delayed gastrointestinal motility, atelectasis, and postoperative pneumonia.[3-5] Furthermore, poorly controlled acute pain is strongly associated with development of persistent incisional pain, which can be devastating for patients. [6, 7]

#### A. Opioids Analgesics and side effects

Although the concept of "multimodal analgesia" of using different drugs with different mode of action to interfere with the pain pathway, such as using non-opioid adjuvants (e.g. NSAIDS, steroids, regional anesthesia) have been developed to improve postoperative pain management, opioids remain the cornerstone of treatment of postoperative pain. Opioids produce analgesia and other effects by binding to specific opioid receptors in the peripheral and central nervous system. Three types of opioid receptors and their subtypes have been discovered: mu, delta, and kappa receptors. The most commonly used opioids bind to mu receptors. The mul receptor is responsible for the production of opioid-induced analgesia, whereas mu2 receptors provoke respiratory depression, cardiovascular effects, and inhibition of gastrointestinal motility commonly seen with opioids.[8-10] Sole reliance on opioids is often inadequate and leads to significant side effects.[11]

Adverse events associated with opioids include an increased risk of postoperative urinary retention (POUR). It has been shown in multiple studies that systemic opioids contribute to urinary retention. Opioids inhibit the release of acetylcholine and thereby decreases the parasympathetic output to the detrusor and thus bladder contractility. This effect is directly related to the dose of opioids given and the opioid sparing multi-modal analgesia has been shown to reduce urinary retention.[12, 13] The true incidence of POUR is unclear but is estimated to vary between 5-70%.[14]

The opiates or its analogues decrease the sensation of bladder fullness by partially inhibiting the parasympathetic nerves that innervate the bladder. In addition, opiates have been shown to increase the sphincter tone of the urinary bladder via sympathetic overstimulation, resulting in increased bladder outlet resistance. The combination of decreased sensation of fullness and increased outlet resistance increase the risk of urinary retention. Studies suggest that the halflife of the opioid used has an impact on urinary function and risk of retention.

Type of opioids used and delivery methods seem to affect the POUR as well. Studies that evaluated orthopedic patients who received fentanyl (short half-life) for post-operative analgesia noted that these patients experienced significantly less risk for urinary retention than those who received morphine (intermediate half-life). Several authors have demonstrated that the risk of retention is also increased in patients using PCA compared to those receiving intermittent IV or IM opioids.

Although the cause of POUR is multifactorial and depends on type and duration of surgery as well as existence of comorbidities, systemic opioids are an important risk factor. Urinary retention requires urethral catheterization and potentially indwelling catheter, leading to patient discomfort, hemorrhage, and increased risk of UTI. Urinary catheters can provide an opportunity for gram negative bacterial infections that can lead to further urological and infectious manifestations (e.g. pyelonephritis, urosepsis, death).[15] Catheter-related UTI is responsible for 13% of 100,000 nosocomial infection related deaths each year.[16] It affects about one million Americans annually and is a significant source of morbidity and mortality. It is the most common "preventable" nosocomial infection that accounts for over \$400 million spent annually in the U.S. alone.[15, 17] Bacteria causing the UTI can potentially hematogenously spread and lead to surgical site infection.[18] Bacterial seeding from UTI is a special concern after certain type of surgery, especially those with prosthetic hardware implanted. For instance, ample evidence related UTI with deep joint infection, hemiarthroplasties and total hip arthroplasties in orthopedic procedures, which carries significant morbidity and financial costs. There is currently no effective medical treatment for POUR from opioids. Previous trials of using phenoxybenzamine to treat POUR have shown mixed results.[19, 20] Naloxone had been tried in the past its reversal of analgesia has limited its usefulness in the clinical setting.[21] Furthermore, naloxone's short half-life of 1-1.5 hours is outlasted by the opioids' effects on the bladder. There is a need for an effective treatment to for urinary retention without mitigating the analgesic effects of opioids.[22]

Postoperative ileus (POI) is common after surgery (incidence of 4.5%), and is a transient loss of peristalsis from inflammatory response and release of endogenous opioids from surgical stress.[23-25] POI contributes to patient discomfort, morbidity, and is the one of the major reasons for prolonged hospital stay and overall health care costs.[25, 26] Opioid receptors, belonging to the G-protein coupled receptor family, are found throughout the enteric nervous system. The actions of opioids on the GI tract are mainly mediated by mu-receptors which lead to: inhibition of release of excitatory acetylcholine, non-peristalsis contractions, decreased water/electrolyte secretion, and increased tone of pyloric and intestinal sphincters.[27-30] The result is an exacerbated postoperative ileus and prolongs the return of bowel function. The true incidence of POI is unknown and varies between the type of surgery but is estimated between 3-15%.[31] Currently there is no promising treatment for POI. Several peripheral opioid antagonists have been developed to treated opioid related POI but with limited application. [32, 33]

Patients in the postoperative period will experience many unavoidable physiologic derangements as a result of anesthesia and surgery. Most studies have examined the effect of anesthetic practices on major clinical outcomes, such as recovery time, cardiovascular complications, stroke, length of hospital stay, and mortality. These endpoints are clinically relevant but do not necessarily reflect the overall state of recovery after anesthesia. Quality of Recovery (QoR), first developed in 2000 by Myles et al., is a psychometric has become an important clinical outcome in anesthesia research because it describes the global quality of life from the patients' perspective after surgery and anesthesia. It indicates the impact of adverse events on such as pain and immobility on the patient's recovery and also indirectly reflects quality of health care. The original quality of recovery 9 (QoR - 9) score was later evolved into a more extensive QoR-40

that has improved reliability and validity. The most recent validated version is a 15-item QoR scale as discussed by Stark et. al.[32] It incorporates five dimensions of health, including patient support, comfort, emotions, physical independence, and pain, and has been proven useful in multiple setting and languages. Quality of recovery will undoubtedly have influence patients' satisfaction of their care, which in the current economic constraints of the healthcare system, and the fact that Centers of Medicare & Medicaid Services are linking hospital reimbursement based on patient's satisfaction, quality of recovery has real financial implications. Opioid analgesia, although an indispensable part of postoperative pain management, is often needed to satisfy the high expectation of pain relief of patients. Overuse of opioids is associated with numerous side effects, (e.g. nausea and vomiting, delay return of bowel function, sleep disturbance, pruritus) which has negative impact on quality of recovery.

#### B. Opioid-related side effects - composite

In addition to urinary retention and postoperative ileus, other common side effects associated with opioids are nausea/vomiting, pruritus, and respiratory depression. Postoperative nausea and vomiting (PONV) affects about 20-70% of postoperative patients and are highly distressing to patients. It is mainly mediated by triggering of opioid-receptors in chemoreceptor trigger zone of the medulla. Opioid induced nausea and vomiting may prolong the recovery room time and a potential hospital stay and lower the degree of patient satisfaction. It has been shown in study that PONV has an impact on quality of recovery. In patients' perspective, PONV is one the most undesirable outcomes in the recovery period. In fact, in one survey, patients were willing to pay out of their own expense to rid of nausea and vomiting completely. Another common side effect of opioid is pruritus, affecting up to 50% patient receiving intravenous opioids and an even higher incidence with neuraxial opioids. The current treatment of pruritus is with antihistamines, 5-HT3-receptor antagonists, opiate-antagonists, propofol, and droperidol, with variable success and with each associated with its side effects. Physicians often respond by dose reduction or discontinuation, which leads to inadequate analgesia and patient discomfort. Another important side effect is opioid induced respiratory depression which is an important source of adverse events in hospitalized patients [33]. Respiratory depression is common in the postoperative period and largely unrecognized, causing significant hypoxemia and potential harm[34].

Worth noting is that opioids might theoretically increases the risk of infections, which might have implications in surgical site infections and infections of hardware in certain surgeries. Opioids have long been recognized as are immune modulators compromising compromise both cellular and humoral immune functions.[35-37] The exact mechanism of this immune modulation is unclear but opioids are hypothesized to act centrally on the hypothalamus-pituitary-adrenal axis and peripherally on the immune cells directly.[38] Opioids bind to 3 major types of receptors: mu, delta-, and kappa-opioid receptors, which are all identified among immune cells, such as PMNs, macrophages, T-lymphocytes, splenocytes, and macrophages.[39] Opioids also alter the macrophage protein expression profile and impair macrophage function including chemo taxis and phagocytosis.[40-42] And finally, opioids reduce B-cell proliferation and antibody production.[43]

Opioid-induced immunodysfunction can potentially lead to surgical site infection. This, a theory is supported by multiple animal studies demonstrating the effect of opioids on mortality.[44] Breslow et al. compared the effect opioids on infection. Mu-receptor knockout and wild-type mice were both pretreated with morphine and were inoculated with Salmonella and the knockout mice were resistant to infection, while the wild-type had 100 percent mortality.[45] Furthermore, there is evidence that increased doses of opioids are associated with wound infections in patients who suffer from major burn injuries.[46] High-dose opioids have been associated with site surgical infection (SSI) after colorectal surgery possibly secondary to immunosuppression.[47] It is plausible to assume that high dose opioids might contribute to SSI.

Duration of hospitalization, or length of stay, is an important indicator of quality of care and inefficiencies of healthcare and has been used by multiple government agencies to measure quality of care from hospitals. The importance of this parameter was demonstrated by the effort to develop new surgical and anesthetic techniques that facilitate recovery in multiple areas of surgery to reduce stay in intensive care unit and length of stay in hospital. It was suggested that one major reason for prolonged duration of hospitalization is from postoperative complications and management of those complications. Prolonged hospitalization also translates to increased healthcare resources. In a study by Collins et al. examining risk factors that contribute to prolonged hospitalization of 23,919 adults undergoing major elective surgery, postoperative adverse events was associated with a high risk of prolonged hospitalization.[48] Opioids-related side effects affect postoperative recovery and contribute to prolonged hospital stay. For example, prolonged ileus has multiple consequences, including decreased patients' comfort, delay of mobilization, and pulmonary complications. For example, patient with opioid-induced ileus significantly stay longer in the hospital after abdominal surgery than those who do not (20 vs. 11 days, p<0.001). Another study of patients who underwent spine surgery and reported urinary retention was associated with longer hospital stay (3.94 d vs. 2.34 d; P=0.005). PONV, a considerable cause of discomfort, should not be taken lightly. PONV has been shown to prolong hospital stay. In severe PONV, it has been documented to cause suture dehiscence and aspiration, which will likely lead to additional treatment and extended hospitalization. In summary, opioid-related side effects hinder recovery and prolongs hospital stay.

In summary, opioids provoke numerous severe complications that cause substantial patient morbidity. They also delay discharge, increase the cost of care, and reduce patient satisfaction. We have a strong need for a peripheral opioid antagonist that could be a part of a multimodal approach to manage and possibly prevent opioid induced side effects that has good oral bioavailability, effective, no effect on centrally mediated analgesia and favorable side effect profile.

#### C. Naloxegol

Peripheral opioid antagonists may prevent some opioid-induced side effects. Naloxegol (marketed as Movantik, by AstraZeneca) is a pegylated (PEG) derivative of naloxone that inhibits  $\mu$ -opioid receptors. The PEG moiety offers several functions including reduced permeability and increased efflux (substrate for P-glycoprotein transporter) across the blood brain barrier making it a mainly peripherally acting  $\mu$  -opioid receptor antagonist. At recommended doses, its ability to only act peripherally allows it to reverse peripheral opioid-related side effects without interfering with opioid-related analgesia or causing withdrawal, as seen with naloxone. The PEG moiety also increases oral bioavailability and allowing oral administration. Naloxegol was approved in 2014 by the U.S. Food and Drug Administration after it passed phase III trials for opioid-induced constipation in adults with chronic non-cancer pain.

Naloxegol binds to all three opioid receptors with greater affinity for  $\mu$ - and K-receptors, the former ( $\mu$ ) being the main receptor implicated in its side effects related to the gut and bladder. The recommended dosage for adults is 12.5 mg to 25 mg daily. After intake orally, it is rapidly absorbed, reaching maximum concentration (C-max) in 2 hours with a second peak appearing 0.4-

3 hours after the first peak. Its absorption is increased by a fatty meal. Its volume of distribution at the terminal phase is 968-2,140 L and it has low plasma binding (~4.2%) in humans. Clearance is mainly by hepatic metabolism (P450-CYP3A) with metabolites whose actions are yet to be defined. A small portion of naloxegol is elimination by renal excretion. The half-life of naloxegol is 6-11 hours.

Naloxegol does not significantly inhibit the CYP1A2, CYP2C9, CYP2D6, CYP3A4 or CYP2C19 or induce CYP1A2, CYP2B6 or CYP3A4 and is thus not expected to affect concentrations of drugs metabolized by these enzymes. Drugs that inhibit CYP3A4 (e.g. ketoconazole, verapamil, cimetidine) might increase Naloxegol concentration, and might need dose adjustment. Naloxegol does not appear to affect the efficacy of other opioids when administered together. In a clinical study of healthy volunteers receiving morphine (5 mg/70 kg), naloxegol has no effect on the pharmacokinetics and metabolic profile of morphine.[49]

Naloxegol is a well-tolerated drug for long-term use (up to 52 weeks) based on clinical trials.[50] The incidence of adverse events ranges from 8-19% and is dose-related.[51] Most adverse events were mild to moderate in intensity and mostly gastrointestinal related including abdominal pain, diarrhea, with a minority experiencing headache and hyperhidrosis.[51] The cardiovascular safety for naloxegol was extensively studied during phase III trials. AstraZeneca organized an independent committee, called Cardiovascular Event Adjudication Committee (CV-EAC) to authenticate major adverse events including MACE (CV death, MI, stroke). Naloxegol was not associated with increased CV risk. The incidence of MACE was 0.6% for placebo versus 0.4% for naloxegol and the incidence of MI was 0.3% for placebo versus 0.2% for naloxegol.[52]

Multiple clinical trials have demonstrated the efficacy of naloxegol including relief of opioid-related side effects while without affecting increasing pain score and daily opioid dose. Two identical phase III, randomized, multi-centered, double blinded studies (KODIAC-04 and KODIAC-05) investigated the efficacy of 12.5 mg/day and 25 mg/day naloxegol versus placebo in adults patients with opioid-induced constipation over a 12 week treatment period.[51] Naloxegol was associated with a significant improvement in bowel function with 25 mg/day and was more effective than 12.5 mg/day. Furthermore, naloxegol did not alter pain scores, daily opioid requirements, or the incidence of opioid-withdrawal across all control and treatment groups.[51]

These findings prove naloxegol's utility as a peripheral opioid antagonist in decreasing opioid's side effects while maintaining analgesia.

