## ii. Exclusion criteria

Subjects should not enter the study if any of the following exclusion criteria are fulfilled:

- 1. Severe hepatic impairment, with/or twice the upper normal levels of liver enzymes
- 2. Severe renal impairment, or creatinine level > 2.0
- 3. History of bladder cancer
- 4. Patients receiving perioperative regional anesthesia blocks
- 5. Presence of a sacral nerve stimulator
- 6. Medications (anticholinergic), conditions or comorbidity causing urinary retention
- 7. Patient with planned requirement of indwelling urinary catheter insertion before or immediately post-surgery due to immobility
- 8. Urinary Tract Infections and other urogenital comorbidity (incontinence, cysto-ureteric reflux, known bladder retention) or conditions which can cause urinary retention
- 9. Severe peptic ulcer disease, diverticular disease, infiltrative gastrointestinal tract malignancies, or peritoneal metastases

- Patients with known or suspected disruption of blood brain barrier, which may include but not limited to: Alzheimer's disease, stroke, poliomyelitis, cerebral palsy, multiple sclerosis, spinal lesions, and Parkinson's disease
- 11. Gastrointestinal obstruction/Gastrointestinal perforation
- 12. Strong CYP3A4 inhibitors (some antibiotics, antifungals, protease inhibitors, and antidepressants), Strong CYP3A4 inducers, Other opioid antagonists
- 13. Hypersensitivity to MOVANTIK (naloxegol) or any of its excipients

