#### **D.** Administration of Naloxegol

The investigational drug for this study is Naloxegol 25 mg per dose to be given once in the morning every day (morning of surgery & on postoperative days- 1 hour before or 2 hours after the morning meal ). The placebo control is equal in size, shape, and color to the active tablets and administered according to the same protocol. The Pharmacy team will have the appropriate randomization in case of a safety or emergency situation, and the study drug label will mention that it is "Naloxegol or Placebo".

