#### E. Protocol

Patients must meet all inclusion and exclusion criteria to be eligible for the study. After eligibility is confirmed, patients will receive complete information about the study both verbally and in writing. Informed consent must be obtained from the patients prior to randomization and study-specific procedures.

Anesthetic management will follow pre-established clinical and institutional guidelines. Patients can be pre-medicated and will receive spinal or general anesthesia per institutional routine according to attending anesthesiologist discretion. Spinal anesthesia will include the standard monitoring for the given operation, and will occur after the electrocardiogram and monitoring equipment are placed on the patient. Prophylactic antibiotics will be given per surgical routine. During the induction of general anesthesia, indwelling urinary catheters will be inserted only in the patients with operation time exceeding 3 h or who required meticulous monitoring of the intraoperative fluid status. Intraoperative and postoperative fluid management will be left to discretion of the clinicians, who will be administrating them using institution standards.

Randomization (1:1) will be web-based and initiated prior to conclusion of surgery; allocation will thus be concealed from investigators. Randomization will be stratified based on chronic opioid use (if present) to ensure balance between treatment groups within chronic opioid users and nonusers. Chronic opioid use will be defined as opioid use for more than 30 consecutive days, at a daily dose of 15 mg or more of morphine or equivalent, within the 3 months before surgery. The treatment groups will be oral Naloxegol and placebo.

Naloxegol or placebo will be administered starting the first morning of surgery and continued for two postoperative days or until hospital discharge (whichever occurs first) with 25 mg (or equivalent size and shape of Placebo). The post-operative study drug doses will be given in the morning 1 hour before or 2 hours after the morning meal. Intraoperative and postoperative pain medications will be left to discretion of the anesthesiologist.

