#### **Enrollment procedures**

The following events will occur in order:

- 1. Screening for eligible patients
- 2. Informed consent
- 3. Randomization

- 4. Administration of study drug starting the morning of surgery and for 2 additional mornings
- 5. Collection of data
- 6. Completion of CRF information

The treatment periods extends from the morning of surgery until the earlier of POD 2 or hospital discharge. Study personnel will follow the study subject until the earlier of POD 2 or hospital discharge. In the case of an adverse event, the study subject will be followed until the resolution of the event.

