## 6. Study Drug handling

## *Identity of investigational product(s)*

Naloxegol 25mg tablets and matching placebo will be used in the study. This material will be supplied by AstraZeneca in unlabeled HDPE bottles containing 18 tablets per bottle. Labels will be prepared at the study site according to Good Manufacturing Practice (GMP) and local regulatory guidelines. Labels will fulfill GMP Annex 13 requirements for labels.

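### The background section warns that verapamil and cimetidine might call for a naloxegol dose adjustment, but exclusion 12 does not evidently cover them and the plan provides only 25 mg: a minor participant-safety gap

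*Combined protocol and SAP*

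**What the plan says.** The Introduction, section C (Naloxegol), describes the elimination route: "Clearance is mainly by hepatic metabolism (P450-CYP3A) with metabolites whose actions are yet to be defined". It then gives the interaction warning: "Drugs that inhibit CYP3A4 (e.g. ketoconazole, verapamil, cimetidine) might increase Naloxegol concentration, and might need dose adjustment". It also gives the dose range: "The recommended dosage for adults is 12.5 mg to 25 mg daily".

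In the exclusion criteria, item 12 reads: "Strong CYP3A4 inhibitors (some antibiotics, antifungals, protease inhibitors, and antidepressants), Strong CYP3A4 inducers, Other opioid antagonists". No other criterion mentions CYP3A4. Item 6, the other criterion that deals with medication, concerns anticholinergics and causes of urinary retention.

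Section D (Administration of Naloxegol) sets one dose: "Naloxegol 25 mg per dose to be given once in the morning every day". Section E (Protocol) sets the duration: "Naloxegol or placebo will be administered starting the first morning of surgery and continued for two postoperative days or until hospital discharge". The enrollment procedures count the doses: "Administration of study drug starting the morning of surgery and for 2 additional mornings". Section 6 (Study Drug handling) sets the supply: "Naloxegol 25mg tablets and matching placebo will be used in the study".

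Section F (Measurements) has the medication list recorded before surgery. Section J (Treatment compliance) lets the investigator have the pharmacy stop dispensing if the drug must be discontinued. It describes no dose reduction.

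**The concern.** The protocol identifies a kind of co-medication that might raise naloxegol concentration and gives three examples. A reader would expect each to be excluded, given a lower dose, or dismissed with a reason. Ketoconazole can be taken as covered, because item 12 lists antifungals. For verapamil and cimetidine the plan does none of these things.

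What is at stake is participant safety. Section C of the Introduction says that adverse events with naloxegol are dose-related. It also ties the drug's mainly peripheral action, without loss of analgesia or withdrawal, to use at recommended doses. Section 4 singles out opioid withdrawal and severe abdominal pain or diarrhea for particular attention. All patients receive postoperative opioids, and chronic opioid users are enrolled as a randomization stratum. Higher exposure in a patient already at the top of the range is what the warning is meant to prevent.

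**Working it through.** No figure in the plan depends on this point, so the check sets the relevant statements side by side. The only arithmetic is the dose count.

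1. **Which drugs does the protocol flag?** CYP3A4 inhibitors, with ketoconazole, verapamil and cimetidine as examples (Introduction, section C). The list is illustrative and the wording is hedged twice.

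2. **Which drugs does it exclude?** Strong CYP3A4 inhibitors, illustrated by some antibiotics, antifungals, protease inhibitors and antidepressants (exclusion 12). Ketoconazole is taken to fall under antifungals. Verapamil and cimetidine are not named and do not evidently belong to any listed class. The documents grade neither drug by strength, so their eligibility is an inference: such a patient appears eligible.

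3. **Could the dose be adjusted?** The recommended range is 12.5 to 25 mg daily. The trial gives 25 mg, the upper limit and twice the lower one (25 / 12.5 = 2). Sections D and E fix that dose, section 6 supplies only that strength with matching placebo, and no section provides a lower one. A reduction is therefore not possible within the plan. Stopping is possible under section J, but that section names no trigger for a drug interaction.

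4. **Would screening catch the patient?** The medication list is recorded, and Table 1 places eligibility screening and drug history at the preoperative visit and on the morning of surgery. The information is available, but no rule tells the screener to act on these two drugs.

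5. **How long would the exposure last?** Morning of surgery plus two further mornings: 1 + 2 = 3 doses at most, or 3 x 25 = 75 mg in total, and fewer if discharge comes sooner.

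6. **What cannot be computed?** The documents give no exposure increase for either drug, no proportion of patients taking them, and no event rate in such patients. The number affected and the added risk therefore remain unknown.

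**The case against.** The strongest reply is that the plan does handle the interaction, at a chosen threshold. It bars strong inhibitors, strong inducers and other opioid antagonists. The warning is an introductory sentence that says only that adjustment might be needed, and it does not tie the 12.5 mg dose to inhibitor use. Excluding strong inhibitors and tolerating others is compatible with it. The documents also report tolerability for up to 52 weeks, mostly mild or moderate events, and no change in withdrawal incidence in the cited trials. Discontinuation, unblinding on clinical grounds and an independent safety board are available as safeguards.

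Much of this stands. It rules out calling the plan contradictory, and it keeps the consequence small. It does not close the gap. The plan never says that the threshold was set with these two drugs in mind, none of the safeguards is specific to them, and the documents do not say that the cited trials included patients taking them.

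The objection is also right about a stronger reading. A reader might infer that a patient whose doses are stopped for an interaction would drop out of observation, because the withdrawal section speaks only of contact for follow-up and safety checks. The documents do not support that. The enrollment procedures follow subjects to postoperative day 2 or discharge, and section 4 follows enrolled patients to discharge. Neither makes this conditional on continued dosing. No text says outright that bladder scans continue after dosing stops, but that question applies to any discontinuation and is not specific to CYP3A4.

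**Conclusion.** The point holds as a minor participant-safety gap. Following the plan as written can give the highest recommended dose to a patient on a drug that the protocol itself flags, with no lower dose provided for.

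This rests on two assumptions: that verapamil and cimetidine are not treated as strong inhibitors under exclusion 12, and that neither falls within its listed classes. If the sponsor regards either drug as strong, that drug is already excluded and only the wording needs clarifying.

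The exposure is at most three doses. A reader might infer that patients would be harmed or that the trial's result is at risk. The documents support neither: they give no exposure increase, prevalence or evidence of harm for these combinations, and the gap has no effect on alpha, power or the primary analysis.

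**What to change.** Extend exclusion 12 to the non-strong CYP3A4 inhibitors that the protocol flags as possibly needing a dose adjustment, and name verapamil and cimetidine. For example: strong CYP3A4 inhibitors, and other CYP3A4 inhibitors for which a naloxegol dose adjustment may be needed, including verapamil and cimetidine. Naming the two drugs gives screeners something definite to check. The general wording is needed because the background list is only illustrative. Screening can use the medication list already recorded.

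The cost is one amended criterion and no new data collection. A few patients, number unknown, become ineligible and must be replaced in recruitment. Supplying 12.5 mg tablets with matching placebo and a dosing rule would also close the gap, but it adds a second strength to supply and blind, which is hard to justify for a gap of this size.
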